Health Link IT will be asked to run a monthly list of potential subjects who are 4-7 years of age and have a clinic appointment for a well-child clinic visit at [name] Pediatrics, University Station, East Towne or West Towne Pediatrics. A letter of introduction will be signed by the primary pediatrician and mailed to each family. The research nurse will put a reminder note on the door after the child is roomed at the clinic to remind the pediatrician that this is a potential subject for the study ([name] and West Towne). The reminder note will have inclusion/exclusion criteria and a brief synopsis of study participation.

During the visit, the clinic staff or pediatrician will ask the family if they are interested in learning more about the study (all sites). If yes, the study nurse will be summoned at the end of the clinic visit to discuss the study with the family ([name], West Towne, and University Station). The handout or flyer will be available to clinic staff to give to families. East Towne families will be directed to contact the research staff directly. If families inquire the reception or nursing staff about the study the study nurse will be on site to answer any questions or clinic staff can direct the family to call the research cell phone.

Optional Stool Collection Sub-Studies

Because the gastrointestinal and respiratory tracts share a common beginning in the mouth and throat (nasopharynx), there is interest in determining whether there are similarities of the microbiome of the NP and feces and if changes that occur at one site are also found in the other. There is also interest in determining whether there are similarities/differences in the microbiome of household members.

Sub-Study 1

Subjects will be invited to participate in an optional sub-study for which we would be collecting a stool sample at every encounter that a nasopharyngeal swab is obtained. We will enroll the first 25 subjects who agree to be in the sub-study. Subjects will be invited during an enrollment visit. At each visit subjects will be assessed for acute diarrhea (4 or more loose stools per day) and antibiotic exposure in the last 4 weeks. If either of these conditions is present, we will not obtain a stool sample.

Sub-Study 2

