Subjects participating in the stool sample collection part of the study will be given instructions and a stool collection kit to take home, collect the sample, and bring to the research staff at the next visit (within 2 days) or the research staff will pick up during a home visit.

b) Surveillance samples. Four visits will be scheduled during the year (February, April, September, and December) to determine the seasonal prevalence of respiratory viruses and microbiota in healthy children. During this visit an interval history will be reviewed and specimens obtained of nasal mucus for virus identification (by nasal wash) and a nasopharyngeal swab. The distal half of the swab will be subjected to DNA extraction for subsequent PhyloChip (and sequence analysis). The remainder will be processed by conventional microbiologic culture methods. The nasal and nasopharyngeal samples will provide information regarding virus identification and bacterial colonization when the subject is healthy. The most recent surveillance data will be used for comparison to data generated during an acute respiratory illness. A letter will be mailed to families to inform them of upcoming clinic walk-in times for the surveillance visits.

Subjects participating in the stool sample collection part of the study will be given instructions and a stool collection kit to take home, collect the sample, and bring to the research staff at the next visit (within 2 days) or the research staff will pick up during a home visit.

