These characteristic clinical presentations that are most likely associated with a bacterial rather than viral infection were adopted and endorsed by a consensus panel in 2003, jointly established by 5 national societies (the American Academy of Allergy, Asthma and Immunology, the American Academy of Otolaryngic Allergy, the American Academy of Otolaryngology – Head and Neck Surgery, The American College of Allergy, Asthma, and Immunology, and the American Rhinologic Society).¹⁷ These clinical definitions for acute sinusitis have now been adopted by the American Academy of Pediatrics and the Infectious Disease Society of America and will appear in both guidelines, which are currently in press. (The PI is an author of both guidelines). In four clinical studies it has been shown that by using these stringent criteria, sinusitis is diagnosed in only 7-8% of respiratory infections presenting to the practitioner who cares for children.^{3,4,6,7}

If a child meets criteria for the definition of sinusitis an additional nasal wash and nasopharyngeal swab will be obtained to identify virus and perform both PhyloChip and conventional culture at that time. A nasal wash and nasopharyngeal swab will also be obtained from children who have recovered spontaneously 10 -14 days after symptoms began. These “recovery” samples will provide information about changes in bacterial community composition that occur following perturbation by viral infection, and will serve as an important comparator to samples obtained during acute sinus infections. Families may choose to have their child seen by the primary pediatrician and if sinusitis is diagnosed the pediatrician may treat with an appropriate antibiotic (standard of care visit). Clinical progress will be tracked until the patient experiences resolution of symptoms.

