Study personnel will send a weekly text to the parent to determine whether there are any URI symptoms have occurred in the last 7 days. The text message will read, “Please call the research staff if your child has had a cough, runny nose, or stuffy nose in the last 7 days. [contact]. Do not respond to this text.” A weekly phone call can take the place of the text message based on parent preference. All subjects included in the study receive their primary and emergency care through the University of Wisconsin Hospital and Clinics. Urgent or immediate care clinics and an “after hours” clinic use the same electronic medical record as does the primary care provider. Thus review of the medical record will permit identification of any episode of sinusitis, URI or other illness for which medical care was sought. Families who are non-responsive after 2 months of follow-up phone calls will be mailed a letter attempting to reconnect with the family and to ascertain whether they wish to continue in the study. A follow-up phone call after 1 week of the mailed letter will be made if we have not heard back from the family.

The family will be mailed a quarterly newsletter that will contain information on colds/sinusitis and an activity for the child. It will also contain a message to call the research staff whenever upper respiratory symptoms are present.

The identity of the viral infection and characteristics of the bacterial colonization of children with an uncomplicated viral URI will be compared to baseline and compared to children whose URI progresses to acute bacterial sinusitis.

Subjects participating in the stool sample collection part of the study will be given instructions and a stool collection kit to take home, collect the sample, and bring to the research staff at the next visit (within 2 days) or the research staff will pick up during a home visit.

d) Study methods – Stool Collection Sub-studies

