Participant will be instructed to stick a paper collection device onto the toilet seat, and void stool into the paper collection device. Participant will then place the stool sample into a sample cup provided using a scoop (also provided), and write the date and time on cup. The remaining stool and paper collection device can then be flushed down the toilet. First bowel movement of the day will be collected, placed in a biohazard bag and refrigerated, at least one day before the next visit. Research staff will transport the samples to the pediatric lab and placed in a -80 freezer. Research staff will batch ship these to UCSF for analysis.

Study methods – Visits

Home visits will be offered for enrollment, acute, recovery, and surveillance. At enrollment, if the family does not have time to enroll after the well-child visit or if the child is upset from having vaccinations, the family can choose to return to the clinic at an arranged time or we will offer a home visit. For acute, recovery, and surveillance families will have the option of coming to the clinic or a home visit. This will ensure completeness of our data.

Study methods - Culture-independent 16S rRNA PhyloChip profiling of nasopharyngeal and stool samples.

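### The antibiotic and diarrhea screen for stool is tied to the visit rather than to when the stool is passed, so the sinusitis-visit stool is open to antibiotic exposure

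*Protocol*

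**What the plan says.** All references are to the Protocol.

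- **When stool is due.** Sub-Study 1 plans "collecting a stool sample at every encounter that a nasopharyngeal swab is obtained". Table 3 accordingly marks stool at the Sinusitis and Recovery visits as well as at entry, surveillance and acute URI.
- **The screen.** Sub-Study 1 states: "At each visit subjects will be assessed for acute diarrhea (4 or more loose stools per day) and antibiotic exposure in the last 4 weeks". A positive answer means no sample: "If either of these conditions is present, we will not obtain a stool sample". Sub-Study 2 repeats the rule for household members.
- **When the stool is passed.** The entry, surveillance and acute-illness parts of section 4 all say that participants "will be given instructions and a stool collection kit to take home, collect the sample". They return it at the next visit, within 2 days, or staff pick it up at home. Section 4.d adds: "First bowel movement of the day will be collected, placed in a biohazard bag and refrigerated, at least one day before the next visit". The family must also "write the date and time on cup".
- **Antibiotics.** Section 4.c lets families see their own pediatrician, and "if sinusitis is diagnosed the pediatrician may treat with an appropriate antibiotic". The start of treatment is not timed against the study visit or the stool.
- **How the stool is used.** Aim 2 includes a pilot number of stool samples in its two groups, URIs that resolve and URIs that progress to sinusitis. The sub-studies' own objective is the relation between changes in the nasopharyngeal and fecal microbiomes. Section 4.e compares sinusitis with no sinusitis by t-test or ANOVA with q-values.

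**The concern.** By adopting a 4-week exclusion, the sponsor treats recent antibiotic use as disqualifying for a stool sample. A look-back made at the visit cannot see a dose taken between the visit and the bowel movement. The sinusitis visit is where such a dose is most likely, because sinusitis is the outcome for which the Protocol foresees antibiotics. Exposure would therefore fall mainly on one side of the two-group stool analysis, and an antibiotic effect on fecal bacteria could be taken for a feature of sinusitis.

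The nasopharyngeal-fecal comparison has a related problem. The swab is taken at the visit and the stool follows, so a dose in between could shift the stool but not the swab it is paired with.

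The diarrhea check has the same timing gap.

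**Working it through.** The Protocol states no figure on this point, so there is none to reproduce. The check sets the timing rules side by side and then scales the result.

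**Step 1. What the screen does under each reading.** Reading A makes the screen at the swab visit, when the kit is handed out. Reading B makes it when the stool is handed in or picked up.

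| When the antibiotic starts | Reading A | Reading B |
|---|---|---|
| Before the sinusitis visit | Not obtained | Not obtained |
| After the visit, before the stool | Accepted although exposed | Refused |
| After the stool, before hand-in | Accepted, unexposed | Refused although unexposed |
| Not at all | Accepted | Accepted |

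Reading A fails in the second row and Reading B in the third. Only a screen referred to the time of the stool sorts both rows correctly.

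**Step 2. Which reading is more natural.** Sub-Study 1 ties stool to encounters with a nasopharyngeal swab, and Table 3 has no hand-over visit. That favours Reading A. Sections 4.b and 4.c do call the return a next visit or a home visit, so Reading B is not excluded.

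**Step 3. Scale.** Inputs: 25 children (Sub-Study 1); 5 URIs per child per year and 8% of URIs complicated by sinusitis (Data Analysis, Aim 1); 15% attrition (Overview).

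- URI episodes: 25 × 5 = 125.
- Sinusitis episodes: 125 × 0.08 = 10, leaving 115 that resolve.
- Children with at least one sinusitis episode, if episodes are independent: 25 × (1 − 0.92^5) = 8.5.
- With 15% attrition: 0.85 × 10 = 8.5 episodes, in 0.85 × 8.5 = 7.2 children.

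**Step 4. Exposed stools.** Let f be the share of sinusitis-visit stools passed after antibiotics start. The Protocol does not give f, so the whole range is shown, on 10 episodes with one stool each.

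| f (assumed) | Exposed stools of 10 |
|---|---|
| 0 | 0 |
| 0.25 | 2.5 |
| 0.5 | 5 |
| 1 | 10 |

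If recovered children are untreated, the spurious difference in a fecal metric is f times the antibiotic effect on that metric. If a share g of the recovered group is also exposed, it is (f − g) times that effect.

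**The case against.** **The timing is not settled.** If hand-over counts as a visit, the 4-week look-back covers the stool and exposed samples are refused. This stands as a possible reading, and it is why the comparison can only be called open to confounding. A reader might infer that it is confounded, but the text does not support that. Reading B also has its own cost, the loss of pre-dose stools, mostly from sinusitis children.

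**Treatment is optional and untimed.** The family may or may not see the pediatrician, who may or may not treat. A child treated before the study visit is caught by the screen on either reading, and that stool is then missing. This stands. A reader might take half or more of the sinusitis stools to be exposed, but the documents give no floor above zero. Nor do they show that recovered children are free of antibiotics: the acute visit also looks for otitis media and pneumonia.

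**Only one time point is affected by the sinusitis antibiotic.** Stools at entry, at surveillance and at an acute visit before the diagnosis are not touched by it. This stands.

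**The stool work is a pilot.** Primary objective 2 names only the nasopharyngeal microbiome, and the stool objective concerns nasopharyngeal-fecal change. This limits the weight of the point. Aim 2 nevertheless lists stool in the two-group analysis, and the stated stool objective is exposed as well.

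**The data to identify exposed stools are largely there.** The cup carries a date and time, medications are reviewed at the acute and sinusitis visits, and the medical record is shared. A SAP could also define exposed stools. This stands in part. Nothing in the Protocol links a first dose to the time on the cup, and a sampling rule that refuses or accepts stools at the wrong moment cannot be repaired at analysis for stools never obtained.

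**Conclusion.** The point holds as a mistimed eligibility rule in an optional sub-study. On the more natural reading, the screen can admit sinusitis-visit stools passed after an antibiotic has started. On the other reading, it discards stools passed before the first dose. Any exposure would fall mainly on the sinusitis side of Aim 2's stool comparison, and it would also affect the paired nasopharyngeal-fecal comparison.

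About 10 sinusitis episodes are expected (8.5 with attrition), and 0 to 10 of their stools could be exposed. That range assumes the Protocol's own rates of URI and sinusitis and one stool per sinusitis visit. It cannot be narrowed, because neither the treated share nor the timing of treatment is given. With so few samples, even two or three exposed stools would matter.

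The incidence estimate and the nasopharyngeal comparison of primary objective 2 are not affected. This is a minor improvement, worth making because it is cheap.

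**What to change.** Reconcile Sub-Study 1, Sub-Study 2 and sections 4.a to 4.d so that the screen refers to the date and time written on the cup.

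- At hand-in or pick-up, record the date and time of any first antibiotic dose, any antibiotic in the 4 weeks before the stool, and any acute diarrhea up to the time on the cup.
- Exclude from the main comparison, or analyse separately as exposed, stools passed after a dose or within 4 weeks of an antibiotic.
- Keep stools passed before the first dose, even if treatment has begun by hand-in.
- Use the same timing for household members in Sub-Study 2. This is for consistency only, since they are not part of the sinusitis comparison.

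The cost is a short question at hand-in and a few lines of text. The downside is that a few sinusitis stools may leave the main comparison. The change concerns sample eligibility and recording only, and leaves treatment as it is.

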These characteristic clinical presentations that are most likely associated with a bacterial rather than viral infection were adopted and endorsed by a consensus panel in 2003, jointly established by 5 national societies (the American Academy of Allergy, Asthma and Immunology, the American Academy of Otolaryngic Allergy, the American Academy of Otolaryngology – Head and Neck Surgery, The American College of Allergy, Asthma, and Immunology, and the American Rhinologic Society).¹⁷ These clinical definitions for acute sinusitis have now been adopted by the American Academy of Pediatrics and the Infectious Disease Society of America and will appear in both guidelines, which are currently in press. (The PI is an author of both guidelines). In four clinical studies it has been shown that by using these stringent criteria, sinusitis is diagnosed in only 7-8% of respiratory infections presenting to the practitioner who cares for children.^{3,4,6,7}

If a child meets criteria for the definition of sinusitis an additional nasal wash and nasopharyngeal swab will be obtained to identify virus and perform both PhyloChip and conventional culture at that time. A nasal wash and nasopharyngeal swab will also be obtained from children who have recovered spontaneously 10 -14 days after symptoms began. These “recovery” samples will provide information about changes in bacterial community composition that occur following perturbation by viral infection, and will serve as an important comparator to samples obtained during acute sinus infections. Families may choose to have their child seen by the primary pediatrician and if sinusitis is diagnosed the pediatrician may treat with an appropriate antibiotic (standard of care visit). Clinical progress will be tracked until the patient experiences resolution of symptoms.

Study personnel will send a weekly text to the parent to determine whether there are any URI symptoms have occurred in the last 7 days. The text message will read, “Please call the research staff if your child has had a cough, runny nose, or stuffy nose in the last 7 days. [contact]. Do not respond to this text.” A weekly phone call can take the place of the text message based on parent preference. All subjects included in the study receive their primary and emergency care through the University of Wisconsin Hospital and Clinics. Urgent or immediate care clinics and an “after hours” clinic use the same electronic medical record as does the primary care provider. Thus review of the medical record will permit identification of any episode of sinusitis, URI or other illness for which medical care was sought. Families who are non-responsive after 2 months of follow-up phone calls will be mailed a letter attempting to reconnect with the family and to ascertain whether they wish to continue in the study. A follow-up phone call after 1 week of the mailed letter will be made if we have not heard back from the family.

The family will be mailed a quarterly newsletter that will contain information on colds/sinusitis and an activity for the child. It will also contain a message to call the research staff whenever upper respiratory symptoms are present.

The identity of the viral infection and characteristics of the bacterial colonization of children with an uncomplicated viral URI will be compared to baseline and compared to children whose URI progresses to acute bacterial sinusitis.

Subjects participating in the stool sample collection part of the study will be given instructions and a stool collection kit to take home, collect the sample, and bring to the research staff at the next visit (within 2 days) or the research staff will pick up during a home visit.

d) Study methods – Stool Collection Sub-studies

Participant will be instructed to stick a paper collection device onto the toilet seat, and void stool into the paper collection device. Participant will then place the stool sample into a sample cup provided using a scoop (also provided), and write the date and time on cup. The remaining stool and paper collection device can then be flushed down the toilet. First bowel movement of the day will be collected, placed in a biohazard bag and refrigerated, at least one day before the next visit. Research staff will transport the samples to the pediatric lab and placed in a -80 freezer. Research staff will batch ship these to UCSF for analysis.

Study methods – Visits

Home visits will be offered for enrollment, acute, recovery, and surveillance. At enrollment, if the family does not have time to enroll after the well-child visit or if the child is upset from having vaccinations, the family can choose to return to the clinic at an arranged time or we will offer a home visit. For acute, recovery, and surveillance families will have the option of coming to the clinic or a home visit. This will ensure completeness of our data.

Study methods - Culture-independent 16S rRNA PhyloChip profiling of nasopharyngeal and stool samples.

Nasopharyngeal swab and stool samples collected in this study will be shipped on dry ice to [name] laboratory at University of California San Francisco. Samples will be thawed on ice prior to centrifugation at 13,000 g at 4 °C for 10 minutes. DNA and RNA will be extracted using a beat-beating/AllPrep kit protocol that we have optimized for nucleic acid extraction from both Gram positive and negative species.¹⁸ DNA will be quantified using a Qubit fluorimeter and the 16S rRNA gene will be amplified using the non-degenerate universal primers (27F and 1492R) across a gradient of annealing temperatures and processed for PhyloChip analysis as previously described¹⁹. To validate array findings, 454-pyrosequencing of the V3-V4 region amplified from the same DNA template will be performed in parallel according to the method of Knight and colleagues.²⁰ In a recent study of 4 pediatric patient stool samples profiled in parallel by what is considered relatively deep 454 pyrosequencing (20,000 reads per sample) and PhyloChip, we demonstrated that at the genus level, 3 of the samples exhibited 100% concordance while the 4th exhibited 96% concordance, i.e., organisms detected by sequencing were also detected by the PhyloChip. However it should be noted that in **all samples**, the **PhyloChip detected 75% more taxa** than these sequencing efforts, representing less abundant members of the estimated 1×10^{14} organisms present in the gastrointestinal microbiota (Lynch et al, unpublished data).

e) Study methods - processing and interpreting the PhyloChip data. Detection and quantification criteria for each taxon detected by the PhyloChip will be conducted as described previously using a positive fraction threshold of ≥ 0.90 .²¹ Statistical analyses using log-transformed fluorescence intensities will be performed in the R environment (www.R-project.org), using the ecological community analysis package *vegan* [version 1.16-1; (129)] to calculate metrics of bacterial community composition, including richness (number of bacterial types present), evenness (relative distribution of species in a community) and diversity (index based on both richness and evenness metrics). Bray-Curtis dissimilarity measures of ecological distance will be calculated before performing non-metric multi-dimensional scaling, a nonparametric ordination method that maps community relatedness based on species presence and abundance. This approach will be used to assess variability in bacterial community structure (particularly to examine if a distinct community composition is associated with differential sinusitis outcomes). Between-group differences (e.g. sinusitis vs no-sinusitis) in both gross community metrics (e.g. richness, evenness and diversity) as well as taxon abundance will be determined by two-tailed *t*-testing or ANOVA and adjusted for false discovery using *q*-values, as we have recently described.¹⁴ Taxa exhibiting *p*- and *q*-values < 0.05 , will be considered statistically significant. Correlation analysis of taxon abundance against that of key sinonasal pathogens (both bacterial and viral) will be performed using the *multtest* package available as part of the Bioconductor suite of analysis programs²² to determine relationships between these species and relative abundance of all other taxa detected. All data will be maintained on a secure server in the Department of Medicine at UCSF, only accessible to those individuals involved in the study. Sequence data generated by 454-pyrosequencing will be used to validate 16S rRNA PhyloChip findings as we have previously described.²³

[figure not shown]
f) Study methods – Conventional bacteriology of nasopharyngeal swabs. Half of the nasopharyngeal swab will be submitted for routine bacterial cultures to the CLIA certified microbiology laboratory of the University of Wisconsin Hospital and Clinics. The plates will be interpreted semi-quantitatively. Isolates of *S.*

S. pneumoniae will be identified by using the optochin disk susceptibility test (Taxo P, Becton Dickinson Microbiology Systems); *S. pneumoniae* isolates will not be serotyped. *M. catarrhalis* will be identified by the API QuadFerm assay (bioMerieux, Inc., Hazelwood, MO, USA), and NT- *H. influenzae* by the Haemophilus ID Quad Plate with Growth Factors (Becton Dickinson Microbiology Systems).

g) Study Methods-Virus Identification The Respiratory Multicode Assay (RMA) is a high throughput and sensitive multiplex PCR based on unique chemistry (Multicode, EraGen Biosciences), and was developed by researchers at the University of Wisconsin-Madison and EraGen BioSciences (Madison WI).²⁴ This state-of-the-art assay detects the following viruses: human rhinoviruses-A, B, and C, enteroviruses, coronaviruses (including OC43, 229, NL63, and SARS), adenoviruses B, C, and E, influenza A and B, parainfluenza viruses I-IV, respiratory syncytial virus A and B, metapneumovirus, and bocavirus. The assay has been validated against standard viral diagnostics.²⁵ Furthermore, rhinoviruses are expected to cause the majority of URIs in the proposed clinical study and the RMA assay has been proven to detect all 100 rhinovirus serotypes as well as the newly discovered C species. Primers have been refined in accordance with sequence information from over 1000 clinical isolates^{26,27}

h) Preliminary Data:

[figure not shown]
i. Bacterial etiology of acute sinusitis in children and response to antimicrobial agents. In a series of studies done between 1981 and 2009^{2,4,5}, Wald and colleagues have provided meticulous data outlining the three major causes of acute bacterial sinusitis in children (*S. pneumoniae*, *H. influenzae* and *M. catarrhalis*) using the gold standard of sinus aspiration. Using stringent clinical definitions of acute bacterial sinusitis, systematic study comparing antimicrobial to placebo has established the benefit of antimicrobials in enhancing clinical cures, reducing clinical failures and shortening the course of the clinical illness.^{4,28}

between these two groups demonstrated that compared to healthy individuals, patients with CRS exhibited dramatic microbiota perturbation characterized by significantly reduced bacterial richness ($p \leq 0.008$; Fig. 3A), evenness ($p \leq 0.001$; Fig 3B) and diversity ($p \leq 0.008$; Fig 3C). These observations were further supported by hierarchical cluster analysis which demonstrated that the majority of healthy subjects clustered in a single tightly-knit group, whose bacterial communities were phylogenetically distinct from patients with CRS, who exhibited clustering of samples into two distinct groups (Group I and Group II; Fig. 3D). This exploratory analysis confirmed that the composition of the sinus microbiota of healthy subjects is distinct from that of CRS. These diverse communities included known pathogenic members of the Pseudomonadaceae, Lachnospiraceae, Ralstoniaceae, Mycobacteriaceae and Helicobacteriaceae

ii. A novel etiology for Chronic Rhinosinusitis (CRS) identified using the 16S rRNA PhyloChip.

In addition to our recent PhyloChip-based study which was the first to demonstrate distinct, niche-specific bacterial communities in paired nasopharyngeal and oropharyngeal samples of healthy adult subjects,¹⁵ we have also examined the sinus microbiota of patients with CRS. Maxillary sinus samples (7 CRS and 7 healthy individuals) were profiled using PhyloChip. Comparative analysis of gross metrics of bacterial community composition

detected in both CRS patients with, and healthy subjects without, sinonasal symptoms. Thus, the mere detection of a suspected or known pathogen at a given niche does not automatically imply pathogenic activity and suggests that the composition of the microbiota at that site may play a large role in defining the activity of community members.

To identify specific taxa that characterized healthy and, more specifically CRS sinus microbiota, we determined which taxa exhibited significantly higher or relative abundance in patients with CRS compared to healthy subject groups. Following correction for false discovery ($p \leq 0.05$, $q \leq 0.05$), a total of 1,482 taxa were detected in significantly lower relative abundance in the sinuses of patients with CRS compared to healthy subjects, underscoring the extent of native microbiota loss from CRS sinus mucosal surfaces. In stark comparison, only a single taxon with the representative species, *Corynebacterium tuberculostearicum* exhibited a significant increase in abundance in patients with CRS ($p \leq 0.03$, $q \leq 0.003$). Figure 4 underscore the clinical significance of these findings, we examined the microbiota data to identify those species that correlated with Sino-Nasal Outcome Score 20 (SNOT-20) symptom severity scores. The SNOT-20 is quality-of-life instrument for sinonasal conditions. A large group of 228 taxa were significantly ($p < 0.05$) correlated with lower SNOT-20 scores (indicative of healthy sinuses). In contrast, the relative abundance of only two taxa was positively correlated with increased symptom severity; both belonged to the Corynebacteriaceae, and the taxon most positively correlated with symptom severity was again represented by *C. tuberculostearicum*.

To confirm our findings and demonstrate that a combination of both depletion of the microbiota and outgrowth of *C. tuberculostearicum* were responsible for the pathology in CRS we developed a novel model of sinusitis in mice characterized by antibiotic-induced depletion of the sinus microbiota and nasal inoculation with *C. tuberculostearicum* (ATCC #35694). Four groups of 5 mice per group (antibiotic treated or untreated with or without inoculation of *C. tuberculostearicum*) as shown in figure 4 were studied. Histological analysis (H&E staining) of the maxillary sinuses of these animals demonstrated airspace obstruction only in mice exposed to a combination of both antibiotic and *C. tuberculostearicum* (Fig. 4A). Subsequent periodic acid-Schiff (PAS) staining specifically for mucin, demonstrated that mice in this group also exhibited evidence of goblet cell hyperplasia and hypersecretion of mucin (Fig. 4B). Compared to all other groups, animals exposed to both antibiotics and *C. tuberculostearicum* exhibited profound goblet cell hyperplasia (Fig. 4D), confirming that the combined conditions of depleted sinus microbiota and *C. tuberculostearicum* inoculation represent key factors defining sinus mucosal health. Data generated in our murine studies suggested that the primary source of mucin secretion originated from goblet cells of the surface epithelium. We therefore examined *MUC5A* expression levels in our healthy subjects and patients with CRS and confirmed that CRS patients exhibited significantly increased *MUC5A* expression, compared to healthy subjects (Fig 4D), corroborating our murine model findings. Finally, we hypothesized that profiling cervical lymph node cytokine production of these mice would provide information on immune responses relevant to patients with CRS. Of the cytokines profiled, only IL-2 exhibited an increase in secretion across treatment groups; mice exposed to a combination of antibiotics and *C. tuberculostearicum* exhibited the greatest increase in lymph node IL-2 expression compared to control animals (data not shown). We subsequently profiled IL-2 expression in our patients with CRS and healthy subjects and demonstrated significantly increased expression in the patients with CRS ($p < 0.008$). Hence by using the PhyloChip to produce standardized microbiota profiles for comparative statistical analyses, we identified and subsequently confirmed in a mammalian model, a novel etiology for CRS that is dependent both on the abundance of a specific *Corynebacterium* species and the composition of the sinus microbiota. These data underscore the ability of PhyloChip to profile bacterial communities and the utility of correlative statistics using these data to identify features of these assemblages responsible for disease (Abreu et al, in review).

i) Data Analysis

Aim 1 - To assess the effects of virus type on progression to acute bacterial sinusitis, the type and number of background asymptomatic viruses, the season, and the interaction of season and background asymptomatic viruses and demographic variables, we will fit a generalized linear model to the URI episode data (1500 observations on 300 children, 0 = non progressing, 1 = progressing) using child as the main sampling unit and assuming a binomial distribution for the data. It is anticipated that the average number of URI episodes per child will be 5 per year. This model accounts for the potential correlation among the multiple episodes in each child. For predictors which take values of yes or no (such as virus type), we will have 80% power to detect the

difference between the percent of a particular virus type equal to 30% for the acute bacterial sinusitis group and 45% for the control group. We will test that rhinovirus is the most common viral URI to predispose to acute bacterial sinusitis using a Chi-squared test for goodness of fit. If rhinovirus accounts for 40% of the URIs leading to sinusitis and the second most common leads to 20% or less then we will have 80% power to conclude that rhinovirus is the most common viral antecedent to acute bacterial sinusitis.

The specimens obtained at baseline and during four other surveillance periods (approximately 1500 - 1800 specimens) will allow us to determine the changes due to season in background level of asymptomatic viral infection and the diversity of viruses. We will use robust multinomial regression using the R package multinomRob that accounts for over-dispersion due to the clustering of the URI episodes within children. This method of modeling multinomial data will allow us to assess the effect of season and the demographic variables on asymptomatic background viruses.

To estimate the incidence of acute bacterial sinusitis as a complication of URI we will use a random effects generalized linear model assuming binomial distribution. We expect a total of 1500-1800 episodes of URI among the children and hypothesize that ABS will complicate 8% of these cases resulting in approximately 120 cases of acute bacterial sinusitis. If the true percent of viral URIs progressing to acute bacterial sinusitis is 8% then 1500 cases will give us 80% power to estimate the incidence with a 95% confidence interval no longer than 2.9%. If we were to observe exactly the 8% incidence the 95% confidence interval would be (6.68%, 9.49%).

Aim 2 - The episodes of acute bacterial sinusitis and uncomplicated URI chosen for PhyloChip analysis will be from two groups. The “acute bacterial sinusitis group” will consist of the first episode of acute bacterial sinusitis occurring among 50 randomly selected children who have one or more episodes of acute bacterial sinusitis. Only the first episode will be eligible to avoid data clustered within child. To avoid running all the PhyloChip analysis at the end of the study we will select the children in groups of 10 evenly spaced over the 52-months of enrollment and follow-up. An additional 50 matched control cases of uncomplicated URI will be selected (10 at a time) from the group of children who have not yet had an episode of acute bacterial sinusitis. The controls will be chosen so that their uncomplicated URI closely matches the case of acute bacterial sinusitis in calendar time. If a control child later develops acute bacterial sinusitis, the control child will become eligible to be chosen for the acute bacterial sinusitis group. If this occurs a different matched control will be chosen as a replacement. This process will result in a few extra PhyloChips being run but is necessary as the processing of PhyloChips is time consuming and cannot be delayed until the end of the study. In addition, the surveillance sample most closely preceding the episode of acute bacterial sinusitis and uncomplicated URI will also be analyzed using the PhyloChip.

